**Schematic of Study Design:**

There will be 4 treatment cohorts, which will be filled sequentially

Cohort	Number of patients	Dose	Treatment cycles
I	3	50 mg	1 (5 days)
II	9	200 mg	1 (5 days)
III*	9	200 mg	2 (5 days each)
IV**	9	200 mg	3 (5 days each)

\*\*\*According to the standard of care clinical practice, a postoperative visit will be done 4 weeks after the cone resection.

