### **3.2 Dosing Rationale**

Although no serious adverse events are anticipated with the doses we propose, the first cohort of subjects will be a run-in of three patients receiving 50mg suppositories. If no mucosal or systemic adverse events are reported, we will proceed with 200mg dosing.

A five-day dosing regimen with a single dose of 200 mg per 24-hour period is selected based on the clinical toxicology and pharmacology database from anti-malarial and cancer trials as well as the performance data presented on the inhibition of HPV infected cells *in vitro* and *in vivo*. We anticipate that intra-vaginal administration of 200 mg Artesunate suppositories to the cervix will provide a local drug concentration well above IC50 of HPV-infected cells. Based on our experimental experience in nonclinical studies, we plan to assess more than one 5-day treatment cycle to explore potential dosing regimens suitable for subsequent phases of clinical studies.

The doses selected for this study are 50 mg and 200 mg. A dose level of 200 mg is equivalent to  $\leq 4\text{mg/kg}$  based on a minimum body weight of 50 kg as a subject inclusion criterion. The proposed dose level should be extremely safe as it is well within WHO recommended pre-referral dose for parenteral Artesunate treatment of severe malaria in young children; that is a single dose of 10mg/kg body weight. The proposed dosing regimen also resembles WHO recommended multi-day dosing regimen for adults and children with severe malaria upon hospitalization; that is 2.4mg/kg IV or IM TID on day 1 (or 7.2 mg/kg) and continued daily dosing at 2.4mg/kg for a total of 7 days [43]. Due to the rapid rate of elimination *in vivo*, negligible systemic accumulation of Artesunate or DHA metabolite is expected over multi-day dosing, especially in the case of local administration.

In summary, local intravaginal administration of Artesunate as a suppository at the highest dose in this study, 200 mg or approximately  $\leq 4\text{ mg/kg}$  is not expected to cause any systemic toxicity. Although no serious adverse events are anticipated with the proposed doses, dose escalation will only occur if no mucosal or systemic adverse events are reported in the first cohort of three subjects who receive the lowest dose. Subjects will be monitored for any unexpected adverse events locally and systemically.

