## 10.2 Intervals Between Visits

The intervals between screening and first administration may be  $3 \pm 2$  weeks, if necessary. A subject is considered enrolled when she receives the first Artesunate suppository at the scheduled Week 0 visit. After the first administration of Artesunate, the time window for each subject to complete 4 remaining daily doses of Artesunate suppositories may be between 4 days and 2 weeks (for example, to minimize potential wash-off of the treatment during a menstrual period). There will be a window of  $\pm 1$  week at weeks 2, 4, 6, 15, and post-operative visit, and  $\pm 2$  weeks at the week 28, and 41 visits.

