**Table 4 – Treatment Cohorts**

Cohort	Number of patients	Dose	Treatment cycles
I	3	50 mg	1 (5 days)
II	9	200 mg	1 (5 days)
III	9	200 mg	2 (5 days each)
IV	9	200 mg	3 (5 days each)

In cohort I, at the first study visit, the subjects will be given a total of five suppositories and applicators. The first suppository will be inserted in clinic, by the patient. Patients will be given diary cards, and will return 1-2 weeks after completing the regimen, for visual assessment of the cervicovaginal mucosa.

In cohorts II-IV, the first study visit will be the same as the first study visit for the run-in cohort. Subjects will return to clinic 1-2 weeks later for visual assessment of the cervicovaginal mucosa. At study week 2, patients enrolled in cohorts III and IV will undergo a visual assessment of their cervicovaginal mucosa and will be given an additional 5 suppositories and applicators. Patients enrolled in cohort III will return to clinic 1-2 weeks later for visual assessment of the cervicovaginal mucosa. At study week 4, subjects enrolled in cohort IV will undergo a visual assessment of their cervicovaginal mucosa, and will also be given five suppositories and applicators. At study week 6, **all subjects** will undergo an interval colposcopic assessment. If their lesions do not appear to be more severe than at study entry, they will return at study week 15. At study weeks 15 and 28, all subjects will undergo colposcopic evaluation. If there is any residual colposcopically abnormal tissue, it will be removed using standard excisional procedures. Peripheral blood and cervical brush specimens will be obtained at study entry, at week 5, at week 15, and at the follow-up visits: postoperative visit, and at weeks 28 and 41.

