### **11.2 Dosage and Administration**

At each dosing visit, after a negative pregnancy test is confirmed, the study physician or nurse will provide five daily vaginal suppositories. During that visit, the subjects will be trained in the vaginal insertion of Artesunate suppositories followed by a tampon, and instructed to administer all daily doses at home at bedtime.

The first 3 study subjects (healthy volunteers with CIN2/3) will receive five (5) daily suppositories that contain 50 mg Artesunate. The 50 mg dose (or  $\leq 1\text{mg/kg}$  for subjects weighing 50kg at minimum) is considerably lower than that used when the anal suppository is intended to deliver a systemic dose of drug for malaria – the 50 mg suppository is recommended by WHO for pediatric care. If no local irritation or systemic toxicities observed in the first 3 patients at 50mg, the dosage will escalate to 5 daily doses of 200 mg per day for the remainder of study enrollments (see treatment cohort table).

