## **12.0 STATISTICAL CONSIDERATIONS**

### **12.1 Study Design/Endpoints/Accrual**

The primary statistical outcome of the trial is safety. The treatment groups will be filled sequentially in a non-blinded manner. Study dropouts will be replaced.

The dose escalation algorithm is described as follows (see Table 4 for dose levels to be tested):

1. A run-in cohort of three patients will be treated with one 5-day cycle of 50mg vaginal suppositories. If no patient has a DLT observed by the cervix check visit after the last suppository, the trial will proceed to the next level.
2. A cohort of 9 patients will be enrolled and treated with one 5-day cycle of 200mg vaginal suppositories. If no patient has a DLT observed by the cervix check after the last suppository, the dose level will be considered tolerable and the trial will proceed to the next level.
3. If exactly one of the 9 patients has a DLT by Week 1-2 after the last suppository, three more patients will be enrolled and treated at the current dose level. If none of the three patients has a DLT by the cervix check after the last suppository, the current dose level will be considered safe and dose will be escalated.
4. If two or more of the 9 or 12 patients have a DLT observed by Week 1-2 cervix check, dose escalation will be stopped. The current dose level will be considered unsafe.
5. A cohort of 9 patients will be enrolled and treated with 2 cycles of 200 mg vaginal suppositories, at 2-week intervals. If no patient has a DLT observed in Cohorts II and III, then the dose level will be considered safe, and the dose will be escalated.
6. A cohort of 9 patients will be enrolled and treated with 3 cycles of 200 mg vaginal suppositories, at 2-week intervals. If no patient has a DLT observed by the cervix check after the last suppository, then the dose level will be considered safe.

With the dose escalation algorithm, there will be less than 9% probability to escalate to the next higher dose level if the DLT rate for the current dose level is 30%.

The maximum sample size for dose escalation is 39. Based on our experience in investigator-initiated therapeutic trials in this patient population at this institution, our anticipated accrual rate is 20-25 patients per year.

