We will correlate immune response with clinical response by looking at the association with disease regression. A logistic regression analysis will be performed with regression as the outcome and baseline and change between baseline and follow-up HPV viral load as predictors, where HPV viral load and the change have been transformed for normality. Using these two predictors, we can assess how change in viral load is associated with clinical response, adjusting for baseline level. Other predictors of interest will also be evaluated, including measures of E7-specific immune response. To explore the association between continuous outcomes of interest and time, the random effects model described above will be used.

The frequency and severity of all toxicities will be tabulated from CRFs and summarized for review in a descriptive fashion. The initial review of toxicity will be completed after the first treatment group has completed the intervention portion of the study (through week 5).

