### **14.0 CLINICAL MONITORING**

This trial will be monitored by the Sidney Kimmel Cancer Center data managers. Data is also reviewed on a bi-weekly basis within the Division of Immunology Clinical Trials Working Group meetings. The principal investigator, study nurse, and data manager participate in these weekly meetings. The JHU and GBMC teams will have weekly conference calls to discuss study progress, and coordinate specimen collection and study activities. The PI and Co-investigator will meet at least monthly. Johns Hopkins Comprehensive Cancer Center (SKCCC) monitoring will occur on a regular basis with the frequency dependent on the subject accrual and the rate of study's progress. This is a DSMP Level II study under the SKCCC Data Safety Monitoring Plan (12/6/12). Data Monitoring of this protocol will occur on a regular basis with the frequency dependent on the rate of subject accrual and the progress of the study. The protocol will be monitored internally at SKCCC by the Principal Investigator and externally by the SKCCC CRO in accordance with SKCCC guidelines. Trial monitoring and reporting will be done through the Safety Monitoring Committee (SMC) at SKCCC. (See Appendix A)

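### Section 12.1 lets the trial move to 200 mg on a DLT-only check that can fall 7 to 24 days before the only named review of all toxicities, and nothing links the two

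*Combined protocol and SAP*

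**What the plan says.** The schematic in Section 1.0 sets the order: "There will be 4 treatment cohorts, which will be filled sequentially". Cohort I is three women at 50 mg; Cohorts II to IV receive 200 mg.

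**The gate.** Section 12.1 step 1: "If no patient has a DLT observed by the cervix check visit after the last suppository, the trial will proceed to the next level". Section 11.8 defines a DLT as a grade 3 toxicity, or an allergic or hypersensitivity reaction of grade 2 or more.

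**When the gate falls.** Section 10.3 says that Cohort I patients "will return 1-2 weeks after completing the regimen, for visual assessment of the cervicovaginal mucosa". Section 10.2, on the time allowed after the first dose: "complete 4 remaining daily doses of Artesunate suppositories may be between 4 days and 2 weeks".

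**The review.** Section 12.4 has the frequency and severity of all toxicities tabulated from the CRFs, then adds: "The initial review of toxicity will be completed after the first treatment group has completed the intervention portion of the study (through week 5").

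**Other statements of the escalation condition.** Section 3.2: "dose escalation will only occur if no mucosal or systemic adverse events are reported in the first cohort of three subjects". Section 11.2: "If no local irritation or systemic toxicities observed in the first 3 patients at 50mg, the dosage will escalate". Section 5.0 likewise makes escalation depend on seeing no untoward effects, mucosal excoriation included.

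**General oversight.** Section 14.0: "Data is also reviewed on a bi-weekly basis within the Division of Immunology Clinical Trials Working Group meetings". It also provides for weekly calls between the two sites and a Safety Monitoring Committee.

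**The concern.** The run-in is there to show whether the suppository irritates the mucosa before the dose rises four-fold. That question is mostly about low-grade local events, which a DLT count does not see. Grade 1 or 2 irritation that is not allergic passes Section 12.1 but fails Sections 3.2 and 11.2. The information those two sections call for is what the Section 12.4 tabulation would supply. Yet that tabulation is dated after week 5, it is described as the initial one, and no section makes Cohort II wait for it. No review is named before the later escalation steps either.

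If Section 12.1 is followed literally, women could begin 200 mg on a DLT count alone, before the all-grade picture from the run-in has been put together. The primary outcome is safety, and Section 3.1 says that no pharmacologic data have been published for this route, so the order of these two steps should be explicit.

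**Working it through.** **The plan's own figure.** Section 12.1 gives a probability below 9% of escalating when the DLT rate is 30%. Exact binomial for the nine-plus-three rule:

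- P(0/9) + P(1/9) × P(0/3) = 0.0404 + 0.1556 × 0.343 = 0.094
- Counting at most one DLT in 12 instead: 0.085

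The figure is reproduced closely: 8.5% on the second count, 9.4% on the literal rule. It describes the nine-patient step, not the run-in. The run-in gate (0 of 3) passes with probability 0.7³ = 0.343 at the same DLT rate. None of this affects the timing below; it shows only that three DLT-free women are weak evidence on their own.

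**Timing inputs**

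- First dose = day 0 (assumption).
- Last of the five doses: day 4 to day 14 (Section 10.2).
- Cervix check: 7 to 14 days after the regimen ends (Section 10.3).
- Week 5 = day 35 (Section 12.4).
- Accrual: 20 to 25 women a year (Section 12.1).
- Adverse events recorded through 30 days after final treatment (Section 11.7).

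Check day = last-dose day + 7 or 14. Gap = 35 − check day. Women starting in the gap = accrual × gap / 365.

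| Last dose | Check after | Check day | Gap (days) | Women, at 20 to 25 a year | 30-day window closes |
|---|---|---|---|---|---|
| day 4 | 7 days | 11 | 24 | 1.3 to 1.6 | day 34 |
| day 4 | 14 days | 18 | 17 | 0.9 to 1.2 | day 34 |
| day 14 | 7 days | 21 | 14 | 0.8 to 1.0 | day 44 |
| day 14 | 14 days | 28 | 7 | 0.4 to 0.5 | day 44 |

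For the last run-in woman the gate therefore precedes week 5 by 7 to 24 days. Her adverse-event window still has 16 to 23 days to run at the gate (34 − 18 = 16 and 34 − 11 = 23; 44 − 28 = 16 and 44 − 21 = 23).

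**Sensitivity to a visit window.** Section 10.2 attaches its ±1 week to named weeks, not to this check. If the check came one week later it would fall on days 18 to 35, and the gap would be 0 to 17 days.

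**Sensitivity to Table 3.** The Wk 2 and Wk 4 columns are footnoted to Groups III and IV. Read that way, Cohort I's first cervix check is at Wk 6 ± 1 week, days 35 to 49. The gate then never precedes day 35 and the gap vanishes. But that reading contradicts the 1 to 2 weeks in Section 10.3. Table 3 also has no week 5 column, although Sections 5.0, 10.3, 10.5 and 12.4 all refer to week 5.

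**Which group is meant.** The Table 3 footnotes use treatment group to mean cohort, so the first treatment group is taken to be Cohort I. If it meant a later cohort, the review would fall later still relative to the run-in gate.

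**The case against.** A reader might infer that women could start 200 mg before anyone has reviewed toxicity from the run-in. The documents do not support that. Step 1 cannot be met unless DLT status is known for all three women at the check. Sections 3.2, 5.0 and 11.2 also bar escalation on irritation or adverse events. The text under Toxicities and Adverse Events has diary cards collected and verified at each visit, and Sections 11.5, 11.9 and 14.0 add immediate reporting of unexpected related serious events, a stopping rule and bi-weekly data review. This stands: the gate is a toxicity assessment, though a limited one.

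The Section 12.4 sentence can also be read as summary reporting. It closes a section on exploratory analysis that calls the treatment a vaccine, and a week 5 endpoint fits three cycles better than a single 5-day cycle, so it may be carried-over text (an inference). That would explain the mismatch. It would not supply the missing link between review and escalation.

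Staggered entry narrows what is unseen. At 20 to 25 a year, women arrive about 15 to 18 days apart, so the first run-in woman is some 29 to 36 days ahead of the third. When the third reaches her check, the first is at about day 40 to 64 and the second at about day 26 to 46. The outstanding follow-up to week 5 belongs to one woman, perhaps two. This also stands, but the review is still dated by the group's completion of week 5, which the third woman sets.

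Finally, sequential filling as stated in the schematic is not an error. The conflict lies between Sections 12.1 and 10.3 on one side and Section 12.4 on the other.

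**Conclusion.** The point holds in a limited form. Read literally, Section 12.1 allows the move to 200 mg on a DLT-only count, 7 to 24 days before the only named review of all toxicities. At the stated accrual that is about 0.4 to 1.6 women. What can be missing at escalation is the all-grade adverse-event review and any events arising after the check.

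The size assumes first dose on day 0, week 5 as day 35, Cohort I as the first treatment group, Section 10.3 timing with no added window, and accrual continuing at the planned rate as soon as the gate opens. On Table 3 the gap is nil, at the price of a contradiction with Section 10.3, so the date of the first escalation decision cannot be fixed from the text. The general meetings in Section 14.0 are not tied to escalation and do not settle it. Few women are affected, but the amendment is cheap and concerns patient protection, so it should be made.

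**What to change.** Reconcile Sections 3.2, 5.0, 10.3, 11.2, 12.1 and 12.4 with Table 3, so that one escalation condition and one gating visit are stated. In Sections 12.1 and 12.4, say that the all-toxicity review is completed on data through the gating visit, before the first dose in the next cohort, and is repeated at each escalation step. Tie it to a visit that Table 3 schedules for that cohort, and replace week 5 with a visit the table contains. Which visit and which escalation condition apply is for the sponsor and investigators to decide.

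The cost is a wording amendment. Held at the gating visit, the review adds little or no delay. If the week 5 date were kept and enrolment waited for it, the run-in step would lengthen by at most 24 days (24 / 7 = 3.4 weeks) on Section 10.3 timing.

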## 2.0 BACKGROUND AND RATIONALE

### 2.1 HPV-associated malignancies of the cervix

Virtually all squamous cervical cancers (SCCx) are caused by a common virus, human papillomavirus (HPV). Exposure to HPV occurs with the onset of sexual activity. While most persons clear their infection without intervention, and without sequelae, a subset do not. Persistent infection with a high-risk HPV type is the proximate cause of SCCs and their precursor intraepithelial lesions, cervical intraepithelial neoplasia (CIN2/3). Other factors contribute to the development of SCC, as viral integration into the host genome is necessary but not sufficient for the initiation and persistence of malignant transformation. Currently there are no available treatments that can eradicate HPV infection. Successful prevention of SCC in infected individuals is based on early detection of preinvasive lesions prior to the development of cancer.

Despite the availability of several, inexpensive, noninvasive screening strategies to detect precursor lesions, the incidence of HPV disease (SCC and CIN 2/3) in women remains high. An effective topical intervention such as current proposal of an intravaginal Artesunate treatment would obviate the need for surgery and prevent progression to SCC. Globally, ten percent of malignancies in women are caused by HPV. Cervical cancer is the second leading cause of cancer death in women worldwide, and in the United States, cervical cancer remains the sixth most commonly diagnosed malignancy among women. Over the past decade, SEER data have documented a 17% increase in incidence in the U.S., normalized for population growth, with a disproportionate increase among young women [5]. Although preventative vaccines that protect against infection with HPV types 16 and 18, the genotypes most commonly associated with squamous cancers, and have been introduced for preteen and teen girls and boys since 2006, their impact has not yet realized as the rates of vaccination remain low in the United States. Recent data indicate that the rate of preventive vaccination in eligible girls, in 2012, was only 33% [6].

The primary strategy to decrease disease burden in HPV-infected individuals is to intervene when premalignant cervical disease, CIN2/3, is detected prior to the development of SCCs. All treatments for CIN2/3, including cryotherapy, laser vaporization, or cone excisions, are ablative and require repeated visits to health care

providers. Because they involve tissue destruction, all current therapeutic options have the potential for adverse sequelae, and furthermore, are not always curative. Among treated CIN2/3 in immunocompetent women, the overall risk of recurrence is less than ten percent when all surgical margins are clear. This risk increases to approximately 25% in women with positive endocervical margins. Women who have undergone cervical conization have three times the risk of cervical stenosis as those who have not [7]. Several authors have documented a significantly increased risk of premature delivery in pregnancies subsequent to cervical conization, and subsequent neonatal low birth weight. [7, 8] Moreover, tissue destruction from therapeutic interventions can make subsequent detection and treatment of recurrent disease more difficult, as the healing process tends to draw the transition zone of the cervical epithelium proximally, into the endocervical canal [9]. While these complications are not insurmountable, an effective local immunotherapy such as intravaginal Artesunate suppositories is clinically meaningful to obviate the need for surgeries.

## **2.2 Noninvasive topical therapy for cervical dysplasia**

The development of a topical therapy for preinvasive CIN2/3 lesions that could be self-administered would be a game-changing treatment option for women with preinvasive HPV disease. A topical treatment option would decrease adverse sequelae related to ablative procedures, decrease visits to specialized health care providers, and result in considerably decreased health care costs. In addition, in many cultures, HPV disease, particularly of the lower genital tract, carries a social stigma [10]. The development of a topical therapy that could potentially be self-administered, would be empowering for women with preinvasive lesions. A topical therapeutic also has the potential to obviate the need for surgery.

